6.9.2 Interruption of administration

The dose may be interrupted, when necessary, until the resolution of toxicity. Depending on when the adverse event is resolved, an interruption in therapy may cause the patient to miss subsequent doses that have been scheduled for that cycle and even delay the start of the next cycle.

Administration of osimertinib (AZD9291) should be permanently discontinued under the following circumstances:

- Interstitial pneumonitis.
- Hepatic insufficiency.
- Gastrointestinal perforation.
- Corrected QT interval prolongation with signs/symptoms of severe arrhythmia.
- Suspension of treatment lasting more than 3 weeks.

If the adverse event that gave rise to the interruption of treatment is resolved within that same cycle, the treatment can be resumed in that cycle. Doses not administered due to toxicity will not be replaced in that same cycle. The need for a dose reduction when treatment is to be resumed should be assessed in keeping with the criteria defined above, unless otherwise agreed upon by the investigator and sponsor. If a dose reduction is made within the cycle, the patient should come to the site to receive a new supply of the drug. If the treatment is interrupted for reasons other than treatment-related toxicity (e.g., surgery not related to cancer) for a period >2 weeks, treatment can only be resumed after consultation with the sponsor.

The appropriate follow-up assessments should be performed until adequate resolution has been reached, in the judgment of the investigator. If these parameters are not met within 3 weeks after the dose interruption (including the scheduled treatment week during which the patient did not receive treatment), then the treatment should be considered permanently discontinued. Treatment can be resumed in cases where patients have recovered from a treatment-related side effect after a period in which treatment has been discontinued for more than 3 weeks or after the cycle has been delayed, but only if treatment offers a clinical benefit to the patient in the judgment of the investigator. In these cases, it is left to the discretion of the investigator after consultation with the sponsor.

If a new cycle is delayed owing to a treatment-related side effect, all procedures other than tumor assessments that are outlined in the protocol and required on Day 1 of the cycle will be performed when treatment with osimertinib (AZD9291) is resumed. Note that the protocol schedule must be followed for tumor assessments. The procedures performed on Day 1 of a new cycle (i.e. physical examination, ECOG performance status, ECG, blood chemistry,

EudraCT No.: 2015-004828-66 Protocol No.: MedOPP112 Protocol date: May 21, 2018

Version 3

blood count) that were performed before awareness of the need to delay the start of the cycle do not need to be repeated (1) if the study staff does not need to determine whether study drug can be resumed and (2) if they were performed within 7 days prior to resuming the study drug.

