6.9.1 Dose reduction

In the event of a significant treatment-related side effect, the osimertinib (AZD9291) dose can be interrupted, delayed and/or reduced, as described below. In the event of multiple side effects, dose change should be based on the worst toxicity observed. Patients are instructed to notify the investigator the moment he/she notices any adverse signs or symptoms.

After an interruption in administration or a delay in a cycle, a dose reduction may be necessary when treatment is to be resumed. No specific dose adjustments are recommended for Grade 1 or 2 treatment-related toxicity.

However, investigators should always use their judgment when treating patients, in accordance with the specific clinical circumstances. A reduction in osimertinib (AZD9291) dose by 1 dose level (Table 2) is permitted, based on the type and severity of the side effect. Patients requiring more than 1 dose reductions will be discontinued from the study and entered into the follow-up phase. All dose changes/adjustments should be clearly noted in the original patient record and in the CRF.

Table 2. Osimertinib (AZD9291) dose reduction

Dosing level	Osimertinib (AZD9291) for 3 weeks
Starting dose	80 mg/day
- 1	40 mg/day
	Discontinue study treatment

Table 3. Osimertinib (AZD9291) dose adjustment after adverse reactions

Organ involved	Adverse Reaction	Dose change
Lung	ILD/Pneumonia	Discontinue the treatment . permanently.
Heart	QTc interval >500 ms at least in 2 different ECGs.	Maintain of osimertinib (AZD9291) until the QTc interval <481 ms or go back to baseline results if they are ≤481 ms and then, restart at a reduced dose (40 mg).
	QTc interval prolongation with signs/symptoms of severe arrhythmia.	Discontinue osimertinib (AZD9291) permanently.
Other	Grade 3 or higher adverse reaction.	Discontinue osimertinib (AZD9291) up to 3 weeks.

EudraCT No.: 2015-004828-66 Protocol No.: MedOPP112 Protocol date: May 21, 2018

Version 3

If the grade 3 adverse reaction improves to grade 2 or lower after osimertinib discontinuation up to 3 weeks	The administration of osimertinib (AZD9291) may start at a normal dose (80 mg) or at a reduced dose (40 mg).
If the grade 3 adverse reaction improves to grade 2 or lower after osimertinib discontinuation up to 3 weeks.	Discontinue osimertinib (AZD9291) permanently.

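### Table 3 and section 6.9.2 name different events for permanent discontinuation, and nothing in the supplied text says how the two relate

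*Protocol*

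**What the plan says.** Two adjacent parts of the protocol tell sites when to stop drug for good.

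- **Section 6.9.1, Table 3.** The lung row, "ILD/Pneumonia", leads to permanent discontinuation. So does the heart row "QTc interval prolongation with signs/symptoms of severe arrhythmia". Everything else goes to *Other*, whose entry condition is "Grade 3 or higher adverse reaction" and whose action is "Discontinue osimertinib (AZD9291) up to 3 weeks". Two further rows follow. Both are conditioned on a grade 3 reaction improving to grade 2 or lower within that period. The first allows restart at 80 mg or 40 mg, and the second requires permanent discontinuation.
- **Section 6.9.2.** The list opens with "Administration of osimertinib (AZD9291) should be permanently discontinued under the following circumstances" and gives five circumstances: "Interstitial pneumonitis", hepatic insufficiency, gastrointestinal perforation, QT prolongation with severe arrhythmia, and a suspension longer than 3 weeks. It attaches no grade to any of them.

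Three other places matter. Both documents define TTF by discontinuation for any cause (protocol section 2.2, SAP section 5.2.2). SAP Appendix 2 leaves it to a case-by-case decision whether a patient who was not withdrawn as the protocol required is excluded from the per-protocol set. Section 6.9 of the protocol tells sites to contact the medical monitor when in doubt.

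**The concern.** Hepatic insufficiency and gastrointestinal perforation end treatment under the 6.9.2 list. A site working from Table 3 finds no row for either and is sent to *Other*, where restart is one of the printed outcomes. The two instructions can therefore give different answers for the same patient.

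The first stake is safety, because a patient could be re-exposed after an event that the protocol elsewhere treats as final. The second is the data. Whether and when such a patient has a TTF event may depend on which page the site used. Whoever decides per-protocol exclusions before database lock also lacks a single rule for judging whether the patient should have been withdrawn.

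**Working it through.** No planned figure is involved, so the check is a side-by-side reading followed by a search for any text that ranks or joins the two.

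**Step 1. Compare item by item.**

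| Circumstance | Table 3 (6.9.1) | List in 6.9.2 | Result |
|---|---|---|---|
| QTc prolongation with severe arrhythmia | Permanent stop | Permanent stop | Agree |
| Lung event | Permanent stop for "ILD/Pneumonia" | Permanent stop for "Interstitial pneumonitis" | Agree in substance for interstitial disease; as printed, a non-interstitial pneumonia appears only in Table 3 |
| Hepatic insufficiency | No row; *Other* if grade 3 or higher | Permanent stop, no grade threshold | Differ |
| Gastrointestinal perforation | No row; *Other* if grade 3 or higher | Permanent stop, no grade threshold | Differ |
| More than 3 weeks off drug | Last row repeats the improvement condition, so non-recovery is not stated | Permanent stop, but a later paragraph of 6.9.2 allows resumption | Each text is unclear in itself; a separate matter |

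The count over the five circumstances is one agreement, one difference in name, two differences in substance, and one time rule that has its own problem.

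**Step 2. Follow one case.** Take a grade 3 gastrointestinal perforation judged to be a reaction to the drug.

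- Under the 6.9.2 list, treatment ends.
- Under Table 3, drug is held for up to 3 weeks. If the event improves to grade 2 or lower, one row allows restart at either dose, and the next row, on the same printed condition, ends treatment.

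Table 3 therefore does not give a clean instruction to restart. It gives two answers, and one of them conflicts with 6.9.2. The follow-on rows speak only of a grade 3 reaction, so for grade 4 Table 3 states the interruption and nothing after it. A later paragraph of 6.9.2 also lets treatment resume within the cycle if the event that caused the interruption resolves, and it makes no exception for the listed events.

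**Step 3. Look for a governing rule.**

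- Section 6.9 refers to the sections that follow, so both texts apply. It does not say whether the lists add together or which prevails.
- Section 6.9.1 invokes investigator judgment, which does not rank the lists.
- Section 5.5 sends the reader to section 7 for discontinuation due to side effects. Section 7 in the supplied protocol is the statistical section, so that reference could not be followed.

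**Step 4. Trace to the analysis.** A permanent stop is a TTF event at that date; a hold followed by restart is not. A restart after perforation is a departure from 6.9.2 and arguably permitted by Table 3, so the per-protocol decision has no fixed reference. The full analysis set, which is the primary population, is untouched, because Appendix 2 does not exclude such patients from it.

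**The case against.** The best answer is that the two texts can be read together. *Other* is a general catch-all and its restart row is permissive. The 6.9.2 list names specific events. A site complies with both by treating the named events as exceptions, and it can call the medical monitor in case of doubt. Nobody is obliged to restart drug after a perforation. This reading is sensible, but the protocol does not state it. The call to the medical monitor helps only a site that notices the conflict, and each text looks complete on its own.

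On the lung event, the objection largely stands. Table 3 concerns adverse reactions, and pneumonia is joined by a slash to ILD in a text with other signs of translation, so it may simply mean pneumonitis. That would remove the lung mismatch and leave the liver and gastrointestinal ones.

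A reader might also infer that a responder stopped under the wrong list would lose confirmation and tip the stage 1 decision, since one patient is 1/21 = 4.8 percentage points and the boundary is 11 of 21. The documents do not support going that far:

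- Protocol section 5.3 schedules a tumor evaluation within 28 days of discontinuation for any reason.
- One paragraph of section 5.2 continues scans every 12 weeks to progression or end of study, although another paragraph there lists treatment discontinuation as an end point for follow-up scans.
- SAP section 5.2 takes best response up to progression and before further anti-cancer therapy, not up to the last dose.
- SAP section 9 records that the interim review supported continuing, and that accrual then closed for a funder's decision.

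**Conclusion.** The inconsistency is real, and it is clear for two events: hepatic insufficiency and gastrointestinal perforation. For the lung event, the printed scope differs but the intended scope may not.

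The consequences that the documents support are inconsistent handling of serious toxicity between sites, TTF events that depend on which text was followed, and no firm basis for one category of per-protocol decision. No effect on the primary analysis or on the stage 1 decision is shown.

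The size cannot be given in patients, because the documents contain no rates for these events. The conclusion assumes that the event is judged a reaction to the drug and is grade 3 or higher, so that Table 3 applies. Section 6.9.1 recommends no specific adjustment for grade 1 or 2 toxicity while the 6.9.2 list has no threshold, so a lower-grade case would conflict too. The documents do not say whether these events would ever be graded that low.

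**What to change.** Reconcile Table 3 with the list in section 6.9.2. Use the same event names in both. Use one defined term for the lung event, and say whether non-interstitial pneumonia falls inside it. Add a sentence stating how the two texts relate. The sponsor's medical team decides which events belong, at what grade, and which text prevails; this review takes no position on that.

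Two neighboring contradictions should be settled in the same edit: the two Table 3 rows that share one condition with opposite actions, and the 3-week rule in 6.9.2 against its own later exception.

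The cost is a protocol wording change to one table and one list, with no added procedures. With accrual closed, the benefit is to any patient still on drug, to the reading of TTF, and to the per-protocol decisions.

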6.10 Possible drug interactions

In vitro data indicate that osimertinib (AZD9291) is mainly metabolized via CYP3A4. Patients should avoid using drugs that are strong inhibitors or inducers of cytochrome p450 (CYP)3A4 during the study active phase. Patients should also avoid grapefruit juice and herbal remedies, including St John's Wort. If their use is essential, patients who are taking them should be monitored closely.

Drugs listed in Appendix 3: Pharmacological interactions with osimertinib (AZD9291) are not permitted due to their drug interaction with the study drug.

Patients who use drugs that are known to prolong the QT interval should be closely monitored using serial electrocardiograms.

7 STATISTICAL CONSIDERATIONS AND STATISTICAL ANALYSIS PLAN

7.1 Sample Size

In the Phase I/II AURA clinical trial, where osimertinib (AZD9291) was administered to patients with advanced EGFR-mutant NSCLC after progression to EGFR TKIs, among the 127 patients with centrally confirmed EGFR T790M mutation, the response rate was 61%. In contrast, amongst 61 patients without centrally confirmed EGFR T790M, the response rate was 21% (15). In the West Japan Thoracic Oncology Group 3405 (WJTOG3405) study, comparing gefitinib with first-line chemotherapy in patients with advanced NSCLC with activating mutations in EGFR, the ORR in the overall population with measurable disease was 62.1% in the gefitinib group and 32.2% in the chemotherapy group. In the North East Japan 002 (NEJ002) study, comparing gefitinib with first-line chemotherapy in patients with advanced NSCLC with EGFR mutations, the gefitinib group had a significantly higher ORR (73.7% vs. 30.7%). In the OPTIMAL study, comparing erlotinib with chemotherapy in patients with advanced NSCLC with EGFR mutations, ORR was 83% for erlotinib and 36% for patients receiving chemotherapy (37). In the LUX-Lung 3 study, comparing afatinib with first-line chemotherapy in patients with advanced NSCLC with EGFR mutations, ORR was significantly higher for patients treated with afatinib compared to chemotherapy according to both the independent evaluation committee (56% and 23%, respectively) and the investigator (69% and 44%, respectively) assessments. In the EURTAC study, comparing erlotinib with first-line chemotherapy in patients with advanced NSCLC with EGFR mutations, ORR was 65.1% in the erlotinib group and 16.1% in the chemotherapy group. A subsequent study assessed the impact of pre-treatment presence of the concomitant EGFR T790M mutation. Among patients treated with erlotinib, the presence of this concomitant mutation was evaluated in 95 patients. ORR was found to be 75% in patients without pre-treatment T790M, compared to 47% in patients with pre-treatment T790M.

This data suggests that excluding an ORR ≤50% while targeting the improvement of the ORR to ≥70% would be a conservative approach to assess the osimertinib (AZD9291) treatment effect in this patient population. Accordingly, this study will test the null hypothesis that the ORR is ≤50% against the alternative hypothesis that it is ≥70%. Applying Simon's optimum 2-stage

Protocol date: May 21, 2018

Version 3

design [Simon 198940], a sample size of 73 patients has power >0.90 to achieve a 1-sided significance level of 0.025. A total of 21 patients will be recruited in the first stage. If there are 11 or fewer responses in these 21 patients, the study will be stopped. Otherwise, 52 additional patients will be accrued for a total of 73 patients. The null hypothesis will be rejected if 45 or more responses are observed in 73 patients. This design yields a type I error rate of 0.025 and a power of 90% when the ORR is 70%.

8.2 Efficacy results

Primary Endpoint

We will describe number and proportion of patients with OR (Objective Response) in the first and second stages. We will estimate the proportion of responders with Clopper-Pearson 95% confidence intervals. We will estimate the uniformly minimum variance unbiased estimator (UMVUE), p-value and 95% confidence interval.

Secondary endpoints:

Number and percentage of patients who obtain Complete Response, Partial Response, Stable Disease and Disease Progression will be provided. The Objective Response Rate (ORR) and its 95% confidence interval (CI) will be calculated. The Disease Control Rate (DCR) and its 95% CI will be calculated. Progression-free Survival (PFS), Overall Survival (OS), Time to Treatment Failure (TTF) and Duration of Response (DOR) will be considered secondary objectives, and as they are time objectives, they will be analyzed using the Kaplan-Meier method. The number and proportion of events and median survival time with their corresponding 95% CIs will be calculated. The analyses will be supported by graphical presentations such as survival plots.

Difference between baseline tumor measurements and those observed throughout the study will be analyzed using the Wilcoxon test. The average percentage of Tumor Shrinkage (TS) observed from baseline to study visits, with their corresponding 95% CIs, will be calculated. Patients with and without different types of EGFR mutation will be compared. For binary outcomes (ORR and DCR), the chi-square or Fisher's exact test will be used. For time objectives (PFS, OS, TTF and DOR), the Kaplan-Meier method and log-rank test will be used. For continuous objectives (percentage of Tumor Shrinkage, TS), the Mann-Whitney U test will be used.

Baseline biomarker levels will be correlated with the clinical response. For binary and continuous results, the Spearman correlation will be used. For time objectives (PFS), the Kaplan-Meier method and log-rank test will be used. The categorization or log-transformation of biomarker levels will be considered.

The feasibility of re-biopsies at the time of progression will be estimated with the number and percentage of patients with rebiopsy and 95% confidence interval.

The presence of mutations and biomarker levels (tissue or blood) will be compared from baseline to time of progression with the Mc Nemar and Wilcoxon tests, respectively.

All efficacy analyses will be exploratory. Positive results in this trial will not confirm treatment efficacy, however, they will indicate that osimertinib (AZD9291) might be considered in the supportive tests.

Protocol date: May 21, 2018

Version 3

8.3 Safety results

Analysis of safety-related data will be considered at three levels:

- First, the degree of exposure (dose, duration, number of patients) will be assessed to determine the degree to which study safety can be assessed.
- Second, clinically relevant tests, concomitant medications and reported adverse events for each study group will be described and compared. For adverse events, severity, expectedness, causality, relationship, body system, action taken, and outcome will be reported.
- Third, serious adverse events, deaths and study discontinuations for each study group will be described and assessed.

8.4 Populations for analysis

Full population for efficacy and safety analysis

It includes all patients who have received the investigational treatment, regardless of the degree of compliance with the protocol.

Per-protocol population (PP):

Per-protocol population includes all patients of the full population for analysis that have not presented any protocol violations that may affect the assessment of the primary endpoint of the study (major protocol violations).

Population for biomarker analysis

All patients included in the full population for analysis whose biomarkers have been assessed.

Efficacy analyses are performed on the full population for analysis and the per-protocol population. The full analysis set population will be the primary population for the efficacy analyses.

The biomarker analysis will be performed on the population for biomarkers. The

safety analysis will be performed for the full analysis population.

8.5 Missing data management

We will report the number of missing values for each endpoint. Patients with missing values in the primary analysis and clinical response outcomes (ORR and DCR) will be considered non-responders. The analysis of time-dependent secondary endpoints (progressions, treatment failures and deaths) will be based on a log-rank test or on Cox regression tests and therefore, will not be affected by the withdrawal of patients (as they would be censored), provided that withdrawals are not related to the prognosis. Patients with missing data regarding endpoints, such as objective response, will be considered patients with no response to treatment. In addition, we will report the reasons for withdrawal of each patient assigned to the treatment.

Protocol date: May 21, 2018 Version 3

8.6 Interim analysis

An interim analysis will be performed when 21 patients have been assessed up to 42 weeks or have withdrawn from the study. The interim analysis will assess the primary endpoint and all the secondary safety and efficacy objectives limited to a window of up to 42 weeks. However, after the database lock at 42 weeks, these patients will continue to be treated and followed up in the study until the patient progresses, dies, discontinues the treatment or completes the study, whichever occurs first.

The efficacy and safety results of the interim analysis will be evaluated by a Scientific Committee that will decide on the suitability of continuing with the study. The study will only be interrupted in case of futility or for safety reasons. For this test, significance levels with p-values with alpha error ≤0.025 will be used.

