3.6 Duration of post-treatment follow-up period (follow-up phase)

The follow-up period is defined as the time elapsed from the last dose of treatment received and death, withdrawal of consent or end of study (EoS), whichever occurs first.

Protocol No.: MedOPP112 Protocol date: May 21, 2018

Version 3

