3.7 End of study (EoS)

The EoS is defined as the Last Patient Last Visit (LPLV) at the end of the follow-up period. This is the last time point for data collection. It can be a clinical visit or a laboratory sample. The EoS will take place in a maximum of 78 weeks after the first dose administered to the last patient enrolled in the study.

However, the interim analysis will assess the primary objective and all the safety and efficacy objectives limited to a window of up to 42 weeks. After database lock at 42 weeks, patients will continue to be treated and controlled until the end of study date (see Section 8.6 Interim analysis).

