5.3 Follow-up phase

Patients will be followed up until the patient dies or the study ends, whichever occurs first. The follow up of all patients will be performed until the last patient completes 78 weeks of treatment, progresses or dies, whichever occurs first.

At these follow-up contacts, information will be obtained on survival status and post-study antineoplastic therapy assessment. Contact by telephone is permitted.

Any events grade ≥2 will be followed until improvement to baseline levels is observed, complete recovery or resolution to grade 1, consent is withdrawn by the patient, patient death or until follow-up is no longer possible.

Protocol date: May 21, 2018 Version 3

 Assessment schedule after progression or study discontinuation for any reason: After progression or study discontinuation for any reason, the following assessments will be performed within a maximum period of 28 days:

- o Anamnesis and symptom assessment.
- Physical examination and measurement of weight, vital signs and ECOG performance status.
- Basic blood test that includes blood count (hemoglobin, hematocrit, RBC count, platelet count and leukocyte count with differential blood count [neutrophils, lymphocytes, monocytes, eosinophils and basophils]) and blood chemistry (sodium, potassium, calcium, chloride, magnesium, uric acid, total proteins, alkaline phosphatase, gamma-glutamyl transferase, lactate dehydrogenase and total bilirubin) with renal function analysis (serum creatinine and creatinine clearance according to the Cockcroft-Gault formula), liver function (AST, ALT, ALP and bilirubin), glucose and coagulation (INR).
- Urine dipstick test for analysis of proteinuria.
- o 12-lead electrocardiogram.
- o Blood sample, which is then sent to central laboratory.
- o Antineoplastic therapy.
- o Assessment of concomitant medications.
- Assessment of adverse events.
- o Tumor evaluation: CT, PET-CT and MRI of at least the chest and abdomen.
- Survival.
- Tumor re-biopsy will be considered (as recommendation only) for analysis of possible mechanisms of resistance and future translational research at the reference laboratory.

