6.6 Interim analysis

An interim analysis will be performed when 21 patients have been assessed up to 42 weeks or withdrawn from the study. The interim analysis will assess the primary endpoint and all the secondary safety and efficacy objectives limited to a window of up to 42 weeks. The first interim report will only include the summary of study accrual, the clinical and demographic summary, the primary efficacy analysis and the report of toxicity. This first report has developed to not delaying the go/not go decision in the first stage. The other results will be presented later. After the database

lock at 42 weeks, these patients will continue to be treated and monitored until progression, death or treatment discontinuation. The decision to stop and continue the trial should be agreed by the steering committee after reviewing the interim safety and efficacy data.

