9. SUMMARY OF CHANGES TO THE PROTOCOL

On December 17, 2018, the AZENT data monitoring committee, on review of the interim analysis, determined that there was evidence to support continued accrual, however the trial was closed to further accrual due to a funder's decision.

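### Protocol 8.6 and SAP 6.6 end post-lock follow-up of stage 1 patients at progression or treatment stop, contradicting survival follow-up elsewhere; applied literally, they would overstate overall survival.

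*Protocol*

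**What the plan says.** Two passages set the rule for stage 1 patients after the 42-week lock.

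- Protocol 8.6: they are treated and "followed up in the study until the patient progresses, dies, discontinues the treatment or completes the study", whichever is first.
- SAP 6.6: "these patients will continue to be treated and monitored until progression, death or treatment discontinuation".

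Other passages set a longer rule for survival.

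- Protocol 3.6 runs the follow-up phase from the last dose to death, withdrawal of consent or end of study.
- Protocol 3.7: "After database lock at 42 weeks, patients will continue to be treated and controlled until the end of study date". It then refers the reader to 8.6.
- Protocol 5.3: "Patients will be followed up until the patient dies or the study ends, whichever occurs first". At these contacts "information will be obtained on survival status and post-study antineoplastic therapy assessment".
- Protocol 5.5 sends patients who stop treatment early to 5.3. It lists only withdrawn consent and loss to follow-up as reasons for leaving the study.
- SAP Table 1 has a follow-up column for the time after progression or end of treatment, running to week 78 from first dose, with survival marked.

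Both documents define OS as time from treatment start to death from any cause. SAP 5.2 leaves censoring to external regulatory guidance and states no censoring date for OS. SAP 9 records that, after the interim analysis, "the trial was closed to further accrual due to a funder's decision".

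**The concern.** Under 8.6 as written, contact with a stage 1 patient can end at progression. Deaths after progression count towards OS, so they would go unseen and the patient would be censored at progression. That is informative censoring: the patients removed have a higher risk of death than those who remain. Protocol 8.5 and SAP 7.6 regard the time-to-event analyses as unaffected by dropout only if dropout has nothing to do with prognosis, and censoring at progression would break that condition. The Kaplan-Meier estimate of OS would be too high, and later anticancer therapy would go unrecorded.

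The closure of accrual adds weight. Stage 1 was to be 21 of 73 patients; it may now be most or all of the OS data. The documents do not give the number finally enrolled.

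**Working it through.** **The plan's own figures.** No OS rate is stated. The stated design figures concern response rate. Exact check: sum over x1 = 12 to 21 of P(X1 = x1) × P(X2 ≥ 45 − x1), with n1 = 21 and n2 = 52. This gives 0.0249 at a response rate of 50% and 0.9004 at 70%, matching the stated 0.025 and 90%. Survival follow-up does not enter this sum.

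**Assumed inputs for OS** (none are in the documents): exponential times; median PFS 9, 12 or 18 months; median post-progression survival 9 or 15 months; 10% of PFS events are deaths. From the documents: 21 patients, lock at 42 weeks, horizon 78 weeks.

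**One case by hand, strictest reading.** Median PFS is 12 and post-progression survival 9 months. The lock falls at each patient's own week 42, and patients who have already progressed are released at the lock.

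- Rates per month: λ = ln2/12 = 0.0578 and μ = ln2/9 = 0.0770, so λ/(μ − λ) = 3.
- True OS: S(t) = e^(−λt) + 0.9 × 3 × (e^(−λt) − e^(−μt)).
- Week 78 (17.94 months): 0.3548 + 2.7 × (0.3548 − 0.2512) = 0.63.
- Week 42 (9.66 months): 0.5724 + 2.7 × (0.5724 − 0.4753) = 0.835.
- After the lock only progression-free patients remain at risk, with death rate 0.1λ. Over 36 weeks (8.28 months) the factor is e^(−0.1 × 0.0578 × 8.28) = 0.953.
- Kaplan-Meier at week 78: 0.835 × 0.953 = 0.80, about 16 points too high.
- Deaths in 21 patients: 21 × (1 − 0.634) = 7.7 true. Seen: 21 × (1 − 0.835) + 21 × 0.5724 × 0.1 × (1 − 0.620) = 3.5 + 0.5, about 3.9 before rounding the parts.

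**All six cases on that reading** (simulation, 400,000 patients each):

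| Median PFS / post-progression (months) | True 78-week OS | Kaplan-Meier under 8.6 | Excess (points) |
|---|---|---|---|
| 9 / 9 | 0.563 | 0.744 | 18.1 |
| 9 / 15 | 0.668 | 0.794 | 12.6 |
| 12 / 9 | 0.634 | 0.796 | 16.2 |
| 12 / 15 | 0.722 | 0.836 | 11.4 |
| 18 / 9 | 0.725 | 0.854 | 12.9 |
| 18 / 15 | 0.792 | 0.883 | 9.1 |

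**Varying the reading and the lock date.** The interim is triggered when all 21 patients have been assessed to 42 weeks or have withdrawn, so earlier entrants are beyond week 42 at the lock. The stage 1 accrual time is also an assumption.

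| Patients who progressed before the lock | Stage 1 accrual | Excess over the six cases (points) |
|---|---|---|
| Released at the lock | none (own week 42) | 9 to 18 |
| Released at the lock | 30 weeks | about 5 to 9 |
| Released at the lock | 52 weeks | 2.6 to 4.0 |
| Stay under 5.3 | none (own week 42) | about 1.5 to 3.4 |
| Stay under 5.3 | 30 weeks | 0.5 to 1.3 |

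A second set of assumed inputs used median PFS 40 to 80 weeks, post-progression survival 26 or 52 weeks, 5% or 15% of first events being deaths, and accrual over 0 or 26 weeks. With release at the lock it gave 6 to 24 points. With follow-up to death or week 78, Kaplan-Meier recovered the true OS in every scenario of that set.

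**Scale.** With 21 patients and true OS of 0.634, the standard error of the 78-week estimate is √(0.634 × 0.366 / 21) = 0.105, about 10.5 points.

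**The case against.** The best reply is that 8.6 was never meant to govern survival contacts. Its end points match the list that protocol 5.2 uses for on-treatment tumour assessment and ECGs in all patients. On that view the sentence says only that the lock does not interrupt treatment, after which the follow-up phase applies as usual. The operational sections (3.6, 5.3, 5.5) and the SAP schedule all keep survival contacts going after progression, and 5.5 does not treat progression as leaving the study. Moreover, 8.6 speaks of patients who continue on treatment, so it hardly describes those who had already stopped before the lock.

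Much of this stands. It makes the bias conditional, and it removes the basis for treating the strictest reading as the expected one. It does not remove the contradiction. The sentence in 8.6 puts treatment and follow-up in the study under one set of stopping events, it is the specific rule for these patients, 3.7 points to it, and SAP 6.6 repeats it. A site or analyst could apply it in good faith.

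The dropout condition in protocol 8.5 and SAP 7.6 is worded for withdrawals, which progression is not. The statistical requirement is the same for any censoring, so the condition would still fail if OS were censored at progression.

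**Conclusion.** The contradiction holds and appears in both documents. Its effect is conditional: none if 5.3 is followed, an overstated OS if 8.6 is applied literally. Under the first set of assumptions the excess at 78 weeks runs from about 0.5 to 18 points; shorter post-progression survival can take it to 24. The direction was the same in every scenario, while the size depends on assumed survival and accrual times and on how 8.6 is read.

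A reader might infer that OS in this trial is too favourable, or that about half the deaths will be missed. The documents do not support either. No passage reports that any patient's contacts were stopped under 8.6, and the loss of half the deaths appears only when patients who had already progressed are released at a lock set at their own week 42.

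OS is secondary, all efficacy analyses are labelled exploratory, and the response-rate test, its type I error and its power are untouched. The point deserves correction because stage 1 may be most or all of the OS data, and survival information not collected before the final lock may not be recoverable.

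**What to change.** Reconcile protocol 8.6 and SAP 6.6 with protocol 3.6, 3.7, 5.3 and 5.5 and with SAP Table 1. State that, for stage 1 patients, survival status and post-study antineoplastic therapy are collected under 5.3 until death, withdrawal of consent or end of study, whether or not the patient has progressed or stopped treatment. Add to the SAP that OS is censored at the last date known alive. If any patient's survival contacts were in fact stopped under 8.6, obtain vital status before the final lock where consent allows.

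The passages on when treatment ends also differ: 8.6 and SAP 6.6 name progression without the CNS exception in protocol 3.2, and 3.7 speaks of treatment to the end of study. The sponsor should reconcile these; no treatment rule is proposed here.

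The cost is wording in two sections and one added sentence. The 12-weekly follow-up contacts are already planned and may be made by telephone, so no new visit is needed. Retrieving vital status would cost a contact only for any patient affected.
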